8.4.3 Classification of an Adverse Event

8.4.3.1 Causality or Relatedness

The Investigator is required to provide an assessment of the relationship of AEs and SAEs to the IP. The Investigator will use clinical judgment to determine the relationship.

An event will be considered “not related” to use of IP if any of the following are met:

- An unreasonable temporal relationship between administration of the IP and the onset of the event (eg, the event occurred either before, or too long after, administration of the IP for it to be considered IP related).
- A causal relationship between the IP and the event is biologically implausible (eg, death as a passenger in an automobile accident).
- A clearly more likely alternative explanation for the event is present (eg, typical adverse reaction to a concomitant drug and/or typical disease-related event).

Individual AE/SAE reports will be considered “related” to use of the IP if the “not related” criteria are not met.

“Related” implies that the event is considered to be “associated with the use of the drug” meaning that there is “a reasonable possibility” that the event may have been caused by the IP (ie, there are facts, evidence, or arguments to suggest possible causation).

Alternative causes, such as underlying disease(s), concomitant therapy, and other risk factors, as well as the temporal relationship of the event to IP administration, will be considered and investigated.

For causality assessment, the Investigator will also consult the IB.

The Investigator must review and provide an assessment of causality for each AE/SAE and document this in the medical notes. There may be situations in which an SAE has occurred, and the Investigator has minimal information to include in the initial report to the Sponsor. However, it is very important that the Investigator always make an assessment of causality for every event before the initial transmission of the SAE data to the Sponsor.

The Investigator may change their opinion of causality in light of follow-up information and send an SAE follow-up report with the updated causality assessment.

The causality assessment is one of the criteria used when determining regulatory reporting requirements.

8.4.3.2 Severity or Intensity

The guidelines outlined in Common Terminology for Adverse Events (CTCAE) v5.0 will be used for assessing the severity or intensity of the event. The general guidelines for assessing the AE grade are provided in [Table 5](#).

Table 5 CTCAE v5.0 General Guidelines

Grade	Description
Grade 1	Mild; asymptomatic or mild symptoms; clinical or diagnostic observations only; intervention not indicated.
Grade 2	Moderate; minimal, local, or noninvasive intervention indicated; limiting age-appropriate instrumental ADL ^a .
Grade 3	Severe or medically significant but not immediately life-threatening; hospitalization or prolongation of hospitalization indicated; disabling; limiting self-care ADL ^b .
Grade 4	Life-threatening consequences, urgent intervention indicated.
Grade 5	Death related to AE.

ADL = activities of daily living; AE = adverse event; CTCAE = Common Terminology for Adverse Events.

The CTCAE v5.0 is dated to 27 NOV 2017.

a Instrumental ADL refers to preparing meals, shopping for groceries or clothes, using the telephone, managing money, etc.

b Self-care ADL refers to bathing, dressing, and undressing, feeding self, using the toilet, taking medications, and not bedridden.

8.4.4 Time Period and Frequency for Collecting AE and SAE Information

All AEs and SAE reporting will begin from the time of signing ICF and continue up until the final study visit at the time points specified in the SoA (Table 1). All events will be followed to resolution or until they are considered a non-clinically significant event.

Investigators are not obligated to actively seek information on AEs or SAEs after conclusion of the study participation. However, if the Investigator learns of any SAE, including a death, at any time after a subject has been discharged from the study, and the Investigator considers the event to be reasonably related to the IP or study participation, the Investigator must promptly notify the Sponsor.

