Note: *Enrolled* means subjects, 'or their legally acceptable representatives', agreement to participate in a clinical study following completion of the informed consent process and eligibility review. Potential subjects who are screened for the purpose of determining eligibility for the study, but do not participate in the study, are not considered enrolled, unless otherwise specified by the protocol. A subject will be considered enrolled if the informed consent is not withdrawn prior to participating in any study activity after eligibility review.

Intervention Groups and Duration

Subjects will receive 200 mg daxdilimab Q12W for 48 weeks (Weeks 0 [Day 1], 12, 24, 36, and 48). Following the final dose administration at Week 48, subjects will be followed up for an additional 8 weeks for a total study duration of approximately 56 weeks.

Investigational Product: Dosage and Mode of Administration

The investigational product (IP) is daxdilimab. Daxdilimab will be provided as a sterile liquid in a 2R glass vial with a nominal 1.0 mL of 100 mg/mL daxdilimab. Daxdilimab drug product is stored at 2°C to 8°C in a refrigerator with adequate temperature monitoring in a location with limited access.

Daxdilimab is to be administered as two 1.0-mL SC injections.

Visit Frequency

The study will be conducted on an outpatient basis. For scheduled study visits, subjects will come to the study sites on 7 occasions: Weeks 0 [Day 1], 12, 24, 36, 48, 52, and 56. For all IP administrations, daxdilimab will be administered by study-site staff at the study site. Subjects will also attend telehealth visits (phone or video call) on 8 occasions: Weeks 4, 8, 16, 20, 28, 32, 40, and 44.

- Study duration: approximately 56 weeks
- Treatment duration and frequency: 48 weeks with in-clinic visits Q12W and telehealth visits Q4W between in-clinic visits
- Follow-up duration and frequency: 8 weeks with 2 visits 4 weeks apart

[figure not shown]
Data Monitoring/Other Committee:

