[REDACTED]	[REDACTED]	[REDACTED]	[REDACTED]	[REDACTED]	[REDACTED]	[REDACTED]	[REDACTED]	[REDACTED]	[REDACTED]	[REDACTED]	[REDACTED]
Investigational Product Administration											
IP administration	X		X		X		X		X		
Safety											
Steroid Taper Discussion	X	X	X	X	X	X	X	X			
Local injection tolerability	X		X		X		X		X		
Concomitant medications	X	X	X	X	X	X	X	X	X	X	X
AEs, SAEs, and/or AESIs	X	X	X	X	X	X	X	X	X	X	X

ADA = anti-drug antibody(ies); AEs = adverse events; AESI = adverse events of special interest; ANA = antinuclear antibodies; C = complement; [REDACTED] d = days; dsDNA = double-stranded DNA; ECG = electrocardiogram; ET = early termination; FACS = fluorescence-activated cell sorting; FSH = follicle-stimulating hormone; HbA1c = glycated hemoglobin A1c; HBV = hepatitis B virus; hs-CRP = high-sensitivity C reactive protein; ICF = informed consent form; IFN α = interferon alfa; Ig = immunoglobulin; INR = international normalized ratio; IP = investigational product; LLOQ = lower limit of quantitation; [REDACTED]; [REDACTED]; MxA = myxovirus resistance protein; [REDACTED]; pDC = plasmacytoid dendritic cell; [REDACTED]; PK = pharmacokinetics; PT = prothrombin time; PtGA = Patient Global Assessment; PTT = partial thromboplastin time; RECAST SLE = Phase 2 Randomized, Double-Blind, Placebo-Controlled Efficacy and Safety Study of Daxdilimab for the Treatment of Moderate to Severely Active Systemic Lupus Erythematosus; RNP = ribonucleoprotein; SAEs = serious adverse events; [REDACTED]; SLE = systemic lupus erythematosus; [REDACTED]

SSB = Sjögren's syndrome-related antibody B; UPCr = urine protein:creatinine ratio; V = visit

a Any procedure that is also completed on RECAST SLE V14 (if performed on the same day as V1 for this study should be utilized for this study and not repeated (Section 5.5).

b Visits 2, 3, 5, 6, 8, 9, 11, and 12 are telehealth visits (eg, phone or video call) (Section 8.1).

- c ECGs should be performed after vital signs are collected ([Section 8.3.3](#)).
- d Vital signs include systolic and diastolic blood pressure obtained after at least 5 minutes at rest in a seated position, heart rate, respiratory rate (breaths/min), and body temperature ([Section 8.3.2](#)).

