4.3 Rationale for Dose

A 200 mg daxdilimab dose administered Q12W has been selected to evaluate whether this decreased frequency of daxdilimab dosing can maintain clinical efficacy and to reduce the risk of safety and tolerability findings in the long term.

Treatment with daxdilimab in a single-blind, Phase 1b MAD study, resulted in a favorable safety profile and rapid and durable depletion of blood pDCs in all subjects receiving a 150 mg Q4W dose. Depletion of blood pDCs remained decreased until 3 months after the final dose when 90% of subjects recovered to within at least 50% of baseline. The 200 mg Q12W dosing strategy will allow for the evaluation of whether blood pDC depletion and recovery reaches a steady state and can be maintained by less frequent dosing.

A treatment period of 48 weeks is considered sufficient to evaluate long-term safety of daxdilimab and the secondary PK/PD outcome measures selected for this OLE study, and current nonclinical ([Section 2.2.4](#)) safety data supports this treatment duration.

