7.3 Lost to Follow-up

A subject will be considered lost to follow-up if the subject repeatedly fails to return for scheduled visits and is unable to be contacted by the study site.

Subjects will be considered lost to follow-up only if no contact has been established by the time the study is completed such that there is insufficient information to determine the participant's status on Day 393 (Visit 15).

The following actions must be taken if a subject fails to return to the clinic for a required study visit:

- The site must attempt to contact the subject and reschedule the missed visit as soon as possible, counsel the subject on the importance of maintaining the assigned visit schedule and ascertain whether the subject wishes to and/or should continue in the study.
- Before a subject is deemed lost to follow-up, the Investigator or designee must make every effort to regain contact with the subject with 3 documented attempts at contact (with one documented attempt being a registered letter/certified mail):
 - Registered letter/certified mail
 - Phone calls, text messages, or emails
 - Consulting publicly available sources, if allowed by local regulations, to determine the status of the subject.

These contact attempts should be documented in the subject's medical record.

- Should the subject continue to be unreachable, the subject will be considered to have withdrawn from the study.

“Lost to follow-up” as a reason for study discontinuation must be documented by time and date of telephone calls, emails, text messages, numbers called, individuals spoken to if not the subject, documentation that a certified/registered letter was sent, and documentation of publicly available sources that were consulted.

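### Active AE, SAE and AESI collection ends 8 weeks after the fifth dose, so the last third of the final 12-week dosing interval goes unobserved with no stated reason

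*Protocol*

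**What the plan says.** The primary endpoint is the incidence of AEs, SAEs and AESIs (Protocol Section 3, Table 2; SAP Section 2.1).

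- **Dosing.** The Synopsis gives five doses, at Weeks 0, 12, 24, 36 and 48. Table 1 places Week 48 on Day 337.
- **Follow-up.** "Following the final dose administration at Week 48, subjects will be followed up for an additional 8 weeks" (Synopsis). The last visit is Visit 15, Week 56, Day 393.
- **Collection window.** AE and SAE reporting starts at consent and is to "continue up until the final study visit" (Section 8.4.4). AESIs share the Table 1 row "AEs, SAEs, and/or AESIs", whose last entry is Visit 15.
- **Afterwards.** "Investigators are not obligated to actively seek information on AEs or SAEs after conclusion of the study participation" (Section 8.4.4). If an investigator learns of a later SAE and considers it reasonably related to the product or to study participation, the sponsor must be told. Events already recorded are followed to resolution or until no longer clinically significant.
- **Analysis.** A TEAE for this study is any AE starting on or after the first OLE dose (Protocol Section 9.3.2.1; SAP Table 4). There is no upper time limit, so the end of collection alone sets the cut-off.
- **Duration of effect.** On the Phase 1b study at 150 mg every 4 weeks, Section 4.3 says: "Depletion of blood pDCs remained decreased until 3 months after the final dose when 90% of subjects recovered to within at least 50% of baseline". Inclusion criterion 4 (Section 5.1) runs male contraception to 3 months after the last dose and equates that with about five half-lives.

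**The concern.** The study is meant to describe long-term safety, and its AESIs include severe viral infection or reactivation and opportunistic infection. The dose given after the longest cumulative exposure has the shortest observation. Collection closes before the next dose would have been due, and before the 3-month point that the protocol uses for drug washout. A new herpes zoster episode ten weeks after dose 5 is an AESI, because Appendix 6 lists zoster in any form. If it were non-serious, nothing in the plan would bring it into the primary endpoint. The protocol justifies the 48-week treatment period (Section 4.3) but not the 8-week follow-up.

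**Working it through.** **1. The plan's own figures.** Day 393 − Day 337 = 56 days = 8.0 weeks, as stated. 195 × (1 − 0.20) = 156 subjects, as stated in Protocol Section 9.5.

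**2. Shortfall against the dosing interval.** 12 weeks = 84 days, and 84 − 56 = 28 days, or 28/84 = 33%. Both visits carry ±7 days, so the time from dose 5 to last collection can run from 42 to 70 days; it stays below 84 even at the extreme. Over five intervals, coverage is (4 × 84 + 56)/(5 × 84) = 392/420 = 93.3%, leaving 6.7% unobserved.

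**3. Shortfall against 3 months.** Taking 3 months as 84 to 91.3 days, the shortfall is 28 to 35 days (33% to 39%). Five half-lives in that time imply a half-life of 16.8 to 18.3 days. At 56 days, 3.3 to 3.1 half-lives have passed, leaving about 10% to 12% of the drug. First-order decline is assumed.

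**4. Person-time.**
- Unobserved if all 156 receive dose 5 (upper bound): 156 × 28/365.25 = 12.0 person-years.
- Unobserved if about 125 do (assumed 20% dropout): 125 × 28/365.25 = 9.6 person-years.
- Collected with no dropout: 156 × 392/365.25 = 167.4 person-years.

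**5. Events.** The documents give no AESI rate, so these are assumptions. With 12.0 person-years unobserved:

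| Assumed AESIs per 100 person-years | Expected in the unobserved time |
|---|---|
| 2 | 0.2 |
| 5 | 0.6 |
| 10 | 1.2 |

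One additional subject with an AESI moves crude incidence by 1/156 = 0.6 percentage points.

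**6. Who is affected.** A subject who stops early has the ET visit and then 8 weeks of follow-up (Sections 4.1 and 7.1). If the ET visit falls *d* days after the last dose, follow-up is about *d* + 56 days, which reaches 84 once *d* is 28 or more. The shortfall therefore falls mainly on those who receive dose 5.

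**7. Link to the exposure-adjusted rate.** SAP Section 4.6 ends exposure 28 days after the last dose. For a five-dose subject first exposed to daxdilimab in the OLE, that is 337 + 28 − 1 + 1 = 365 days, while TEAEs are counted to Day 393. So 28 days of event counting already lie outside the denominator of the rate in SAP Section 4.9.1. Collecting to Day 421 (337 + 84) without changing Section 4.6 would make that 56 days.

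**The case against.** The strongest reply is that this is a consistently stated design choice with small consequences. Much of it stands.

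- **No contradiction.** A reader might infer that the plan contradicts itself. It does not: 8 weeks is stated the same way in the Synopsis, Table 1, Sections 4.1 and 8.1, and SAP Section 2.2, and nothing requires follow-up to match the dosing interval.
- **pDC recovery.** A reader might take 3 months as the established recovery time for this regimen. The figure comes from three doses of 150 mg every 4 weeks, and Section 4.3 says that 200 mg every 12 weeks is being studied partly to learn how depletion and recovery behave. The single-dose study (Section 2.2.5.1) makes slow recovery plausible: the median passed 50% of baseline at Day 85 after 50 mg, and the time could not be determined for 150 mg. It does not supply the missing figure.
- **Not a blind spot.** Weeks 9 to 12 after a dose are observed after doses 1 to 4: 4 × 156 × 28/365.25 = about 48 person-years with no dropout. Only the last repeat is missing.
- **Reporting does not stop altogether.** Open events are followed. Related SAEs that become known must be reported, and Section 8.4.3.1 makes related the default unless a not-related criterion is met.
- **Malignancy.** Four more weeks would add little, and Section 10.2.2 lists invasive or malignant cancers among events usually considered serious. The case rests on the infection AESIs.
- **No inference at stake.** The analysis is descriptive, with no hypothesis test.

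What remains is an unexplained gap in the primary endpoint that is cheap to close. Correcting any contraception or pregnancy window would leave it open.

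**Conclusion.** The point holds as a modest limitation. Active collection ends 56 days after dose 5, against an 84-day interval and the protocol's own 3-month washout figure, and no reason is given. New non-serious AEs and AESIs, unrelated SAEs and unreported events in the last 28 days of the final interval are lost. The size is at most about 12 person-years, or 6.7% of five full intervals, assuming that all 156 eligible subjects enrol and receive dose 5. The corresponding 0.2 to 1.2 AESIs rest on assumed rates, held constant over the interval. Applying the pDC recovery time to 200 mg every 12 weeks is an extrapolation. The documents do not support a conclusion that the primary endpoint is materially biased or that late post-dose risk goes unstudied.

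**What to change.** Keep AE, SAE and AESI reporting open until 12 weeks after the last dose, and add one telehealth contact at that point for AEs and concomitant medications, of the kind already used between Weeks 4 and 44. Align the Synopsis, Table 1, Sections 4.1, 7.3 (which refers to Day 393), 8.1, 8.4.2 and 8.4.4, and SAP Section 2.2.

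In SAP Sections 4.6 and 4.9.1, make the person-time denominator of the exposure-adjusted rate cover the same period in which TEAEs are counted. This part is needed even if follow-up stays at 8 weeks, and the extension should not be made without it.

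The cost is a protocol amendment, one extra call per participant, and last-subject-out about 4 weeks later. A call would not pick up events found only by laboratory testing, such as hepatitis B reactivation, so part of the gap would remain.

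If the sponsor keeps 8 weeks, it should give the reason in the protocol and state in the SAP and the study report that the last 4 weeks of the final dosing interval were not actively observed.

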8.4.5 Method of Detecting AEs and SAEs

Care will be taken not to introduce bias when detecting AEs and/or SAEs. Open-ended and nonleading verbal questioning of the subject is the preferred method to inquire about AE occurrences.

8.4.6 Follow-up of AEs and SAEs

The Investigator is responsible for appropriate medical care of subjects during the study. After the initial AE/SAE report, the Investigator is required to proactively follow each subject at subsequent visits/contacts. All events will be followed to resolution or until they are considered a non-clinically significant event, or the event is otherwise explained, or the participant is lost to follow-up (as defined in Section 7.3).

Additional information regarding follow-up procedures is provided in Appendix 2, Section 10.2.3.

8.4.7 Regulatory Reporting Requirements for SAEs

Any death, life-threatening event, or other SAE and any pregnancy, overdose, and AESI experienced by a subject during the course of the study, whether or not judged related to the

investigational product, must be reported within 24 hours of knowledge of the event by entering the information into the eCRF. If unable to access the eCRF, the event must be reported by submitting the completed SAE form via email or fax to the contact numbers provided below.

- Email: [contact]
- [contact]

The event must be documented in source documentation and the eCRF. The following steps will be taken to report promptly and document accurately any SAE, whether or not it appears to be related to IP:

1. Report the SAE to the Sponsor by entering the information into the eCRF within 24 hours after becoming aware that a subject has experienced an SAE. If unable to access the eCRF, the event must be reported by submitting the completed SAE form by email to [contact] or fax within 24 hours after becoming aware that a subject has experienced an SAE.
2. Perform appropriate diagnostic tests and therapeutic measures, and submit all follow-up substantiating data, such as diagnostic test reports, hospital discharge summaries, and autopsy report to the Sponsor's representative.
3. Respond in a timely manner to any queries from Sponsor regarding the SAE.
4. Conduct appropriate consultation and follow-up evaluation until the SAE is resolved, stabilized, or otherwise explained by the Investigator.
5. Review each SAE report and evaluate the relationship of the IP.
6. Each Investigator must report all AEs or SAEs to its Institutional Review Board (IRB) or Independent Ethics Committee (IEC) in accordance with IRB or IEC requirements.

After receipt of the initial report, the information will be reviewed, and the Investigator may be contacted with requests for additional information or for data clarification.

Follow-up will be obtained via the eCRF, fax, or email, as necessary, until the event resolves or attains a stable outcome. Sponsor or designee is responsible for the preparation of MedWatch 3500 A/Council for International Organizations of Medical Sciences I forms and analysis of similar events for individual occurrences (to be submitted as Investigational New Drug [IND] safety letters to the FDA and Investigators according to Title 21 of the Code of Federal Regulations [21 CFR 312.32] by the Sponsor).

Additional information regarding SAE reporting via an electronic or paper data collection tool is provided in Appendix 2, [Section 10.2.4](#).

8.4.8 Pregnancy

Pregnancy in a woman who has received IP must be reported to the Sponsor from time of signed ICF until end-of-study follow-up or 3 months (approximately 5 half-lives) following the last dose of IP in case of early withdrawal. The Investigator must report the pregnancy to the Sponsor or representative as if it were an SAE (ie, within 24 hours of learning of the pregnancy) Refer to [Section 8.4.7](#) for additional information.

Subjects who become pregnant during the study period must not receive additional doses of IP. These subjects will discontinue IP and follow the IP discontinuation procedures ([Section 7.1](#)). While pregnancy itself is not considered to be an AE or SAE, any pregnancy complication or elective termination of a pregnancy for medical reasons will be reported as an AE or SAE.

Abnormal pregnancy outcomes (eg, spontaneous abortion, fetal death, stillbirth, congenital anomalies, ectopic pregnancy) are considered SAEs and will be reported as such.

The subject will be followed to determine the outcome of the pregnancy. The Investigator will collect follow-up information on the subject and the neonate, and the information will be forwarded to the Sponsor after the outcome.

Should the Investigator become aware of a pregnancy in the partner of a male study subject who has received IP, this should be reported to the Sponsor within 24 hours of knowledge of the event (refer to [Section 8.4.7](#) for additional information). The Sponsor will endeavor to collect follow-up information on such pregnancies, provided the partner of the study subject provides consent for disclosure of their information.

Any poststudy pregnancy-related SAE considered reasonably related to the IP by the Investigator will be reported to the Sponsor as described in [Section 8.4.7](#). While the Investigator is not obligated to actively seek this information in former study subjects or pregnant female partner, he or she may learn of an SAE through spontaneous reporting.

